For the product of the ratio of average glucose (Week 12/Baseline) and ratio of average insulin use (Week 12/Baseline), glucose AUC after MMTT, C-peptide AUC after MMTT and arginine challenge test (for a subset of subjects in Part A who were enrolled prior to Protocol Amendment #1), fasting glucose, insulin, C-peptide, GLP-1, and glucagon, a repeated measures analysis of covariance will be performed, as well as before and after treatment analysis.

For comparison of proportion of subjects that achieve HbA1c reduction of $\geq 0.4\%$ in the REMD-477 and placebo groups, chi-square test will be conducted.

For a subset of subjects in Part B, the change in hepatic fat content from baseline will be calculated for each subject and the mean change will be calculated for each treatment arm.

Study Disposition and Demographic Data

The number of subjects who receive investigational product and complete the study will be summarized. A list of subjects who withdraw early will be provided. It will include the reason and timing of the withdrawal. Similarly, the reason any subject is excluded from an analysis set will also be provided. In addition, significant known protocol deviations will be noted for individual subjects.

Age, race, sex, height, and weight will be summarized for all the subjects receiving investigational product using descriptive statistics.

Population Pharmacokinetics

Serum REMD-477 concentrations will be determined using a validated assay. A population

PK analysis will be performed from REMD-477 concentrations evaluated on Days 1, 8, 29, 57, 85, and 106.

Safety Analysis

Adverse Events

All subjects who receive at least one dose of REMD-477 or placebo will be included in the safety analyses. The number of subjects reporting treatment-emergent adverse events will be determined overall, by preferred term, and by system organ class according to the current MedDRA terminology. The number and percentage of subjects reporting adverse events will be evaluated for each treatment and will also be tabulated by relationship to study drug.

Adverse events resulting in treatment discontinuation will be identified.

Vital Signs

Vital signs will be listed and reviewed for each subject. Summaries of heart rate and blood pressure data over time and change from baseline will be provided. Depending on the size and scope of change in other vital signs, summaries may be provided for this data.

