9 DEFINITION OF ANALYSIS POPULATIONS

The analysis populations apply to both Parts A and B separately.

The **All Subjects Population** will consist of any subjects who enrolled on to the study (signed informed consent) and had study assessments recorded on the database as per the protocol.

The **Efficacy Population** will consist of all subjects who received at least one dose of REMD-477 and have evaluable average daily insulin use data.

The **PD Population** will consist of all subjects who received at least one dose of study drug (REMD-477 or placebo) and have evaluable PD data.

The **Safety Population** will consist of all subjects who received at least one dose of study drug (REMD-477 or placebo) and have at least one post-dose safety assessment.

The **PK Population** will consist of all subjects who received at least one dose of REMD-477 and have evaluable PK data.

All protocol deviations that occur during the study will be considered prior to database lock for their severity/impact and will be taken into consideration when subjects are assigned to analysis populations. Details of subject assignment to the analysis populations will be summarized and listed.

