11 INTERIM ANALYSES

No formal interim analysis is planned; however, an unblinded preliminary analysis of the safety and pharmacodynamics data may be completed for internal business decisions and to help with planning future studies for REMD-477. This unblinded analysis may take place after the 30th and 60th subject enrolled in this study completes the Day 85 visit. Unblinding of subject treatment assignment will be limited to the designated unblinded Covance team and REMD study teams; Investigators and subjects will remain blinded. The unblinded team from Covance is separate to the study team that will be responsible to analyze the data post database lock.

The preliminary analyses may be shared with the Investigators in an aggregate form such that blinding is maintained.

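### SAP 9 lets protocol deviations, judged without stated criteria or blinding, influence who enters the single set that carries the primary test

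*SAP*

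**What the plan says.** SAP Section 9 states: "All protocol deviations that occur during the study will be considered prior to database lock for their severity/impact", and that these deviations "will be taken into consideration when subjects are assigned to analysis populations". The rule is written for all analysis populations. The section adds: "Details of subject assignment to the analysis populations will be summarized and listed".

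The Efficacy Population is made up of subjects who "received at least one dose of REMD-477 and have evaluable average daily insulin use data". The SAP does not define evaluable. The Safety Population is made up of subjects who received REMD-477 or placebo "and have at least one post-dose safety assessment". Protocol Section 10 (Safety Analysis) has no such condition: "All subjects who receive at least one dose of REMD-477 or placebo will be included in the safety analyses".

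On exclusions, Protocol Section 10 promises that "the reason any subject is excluded from an analysis set will also be provided", without saying what would justify one. SAP Section 11 allows unblinded preliminary analyses, with access to treatment codes "limited to the designated unblinded Covance team and REMD study teams". It also says that the unblinded CRO team is separate from the team that will analyse the data after lock.

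**The concern.** Deviations happen after randomization, and some can depend on how a subject responds to treatment or tolerates it. Use of a prohibited glucose-lowering drug and missed doses are examples. If such subjects are removed case by case, the groups compared are no longer the groups that were randomized.

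Three features make this matter here:

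- There is one Efficacy Population. No full-analysis or per-protocol set is defined. The only sensitivity analysis of the primary endpoint (SAP 10.3.4.2) changes the scale to percentage change, not the set of subjects. A removal therefore enters the Hochberg-tested comparison directly.
- No document says which deviations exclude a subject, who decides, or that the decision is made without knowledge of treatment.
- Sponsor study teams may hold treatment codes from the preliminary analyses. SAP Section 12 refers to a first interim of Part A, so at least one such look took place.

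Two drafting problems in the same section add to this. Read literally, the Efficacy Population excludes placebo. The Safety Population departs from the protocol, and SAP Section 12 does not list that as a change, although SAP Section 4 says substantial differences will be identified.

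**Working it through.** **1. The plan's own sample size.** Inputs from SAP Section 8: CV about 36%, difference 30%, power 0.8, alpha 0.05 (taken as two-sided), at least 22 needed and 25 planned per group in each Part.

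n = 2 × [0.36 × (1.960 + 0.842) / 0.30]² = 22.6, which rounds up to 23. This agrees with the stated 22 to within one, so the sample size is not in dispute. The margin over 22 is 3 per group (3/25 = 12%).

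**2. Cost in power when removals are unrelated to outcome.** Normal approximation, equal arms:

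- 25 per arm: 0.838
- 22 per arm: 0.789
- 20 per arm: 0.750

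The comparison is not biased, but the margin is used up.

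**3. Possible bias when removals are related to outcome.** The documents give no exclusion counts, so everything here is assumed: true effect zero, 25 per arm, SD of change 36 percentage points, removals from one active arm only and tending to be its less favourable outcomes, two-sample t-test at 0.05, 40,000 simulated trials per case. Negative bias favours the drug.

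| Link between removal and outcome | Removed of 25 | Bias (points) | Two-sided type I error |
|---|---|---|---|
| None | 3 | 0.0 | 5.1% |
| None | 5 | −0.2 | 4.8% |
| Correlation 0.3 | 3 | −2.4 | 5.7% |
| Correlation 0.3 | 5 | −3.6 | 6.2% |
| Correlation 0.5 | 3 | −3.9 | 6.9% |
| Correlation 0.5 | 5 | −6.05 | 8.9% |
| Extreme: the worst outcomes removed | 3 | −7.7 | 13.3% |
| Extreme: the worst outcomes removed | 5 | −12.0 | 23.6% |

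The departures from zero bias and 5% error in the first two rows are simulation noise.

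**4. Closed-form check.** Suppose the removed subjects average 27 points (27/36 = 0.75 SD) worse than their arm. With removed fraction f, shift = 27f/(1 − f), SE = 36 × sqrt(1/n_active + 1/25), and error = P(|Z + shift/SE| > 1.96).

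- 2 removed (f = 0.08): shift 2.3, SE 36 × sqrt(1/23 + 1/25) = 10.4, ratio 0.23, error 5.6%.
- 3 removed (f = 0.12): shift 3.7, SE 36 × sqrt(1/22 + 1/25) = 10.5, ratio 0.35, error 6.4%.
- 5 removed (f = 0.20): shift 6.75, SE 36 × sqrt(1/20 + 1/25) = 10.8, ratio 0.625, error 9.6%.

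For moderate association and 3 to 5 removals, both methods give about 6–10%.

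**5. Text comparison.** The PD and Safety definitions in SAP 9 name REMD-477 or placebo. The Efficacy definition names REMD-477 only, yet SAP 10.3.4.2 tests each dose against placebo, so the primary test cannot be run on the set as written. SAP 10.1 also omits Efficacy when it names the relevant populations. For safety, the protocol requires one dose, while the SAP requires one dose plus a post-dose assessment, subject to the deviation review.

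**The case against.** The strongest reply is that the SAP says deviations are considered, not that they exclude anyone. The review precedes lock, the trial is double-blind, assignments are listed, and the protocol promises a reason for each exclusion. The CRO team that analyses the final data is separate from the unblinded one. All of this is true. It makes removals visible and narrows the opportunity for bias. It does not supply criteria or a blinded review, and it does not give a second set against which to check the result.

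Several stronger readings are tempting but unsupported:

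- A reader might infer that deviations decide membership. The wording is weaker than that.
- A reader might infer that unblinded sponsor staff choose the sets. No document says so. The gap is that nothing rules it out.
- A reader might count insulin changes outside the titration algorithm as deviations. Protocol Section 7 allows basal and bolus adjustment at the investigator's discretion, so these are permitted.
- A reader might assume that subjects with missed doses or rescue medication are dropped. Protocol Section 8 asks subjects who stop product to continue observations, and Section 6 lets rescue medication for hyperglycemia be reviewed for continuation in the study. The protocol leans towards keeping them.
- A reader might expect dosed subjects to vanish from the safety denominator. Protocol Section 7 places discharge on Day 1 after post-dose procedures, with a phone call 3–4 days later, so almost every dosed subject should have a post-dose assessment.

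The objection to the numbers also stands in part. One-arm removal and the strength of selection are assumptions. The 36% is the CV of daily insulin requirement, not a documented SD of change, and the primary test uses absolute change.

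**Conclusion.** The concern holds as a gap in the rule, not as a demonstrated bias. SAP 9 permits discretionary removals after randomization from the only set used for the primary test, with no criteria and no stated blinding.

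The size of any bias cannot be derived from the documents. It is zero if removals are unrelated to outcome, and balanced removals across arms would largely cancel. It would run against the drug if better responders were removed. The 6–10% figure is an illustration for one test at 0.05 under the assumptions shown. It is not the error rate of the trial, which uses Hochberg across two doses.

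The omission of placebo from the Efficacy Population is a plain wording defect. Since the whole plan compares with placebo, it is more likely a slip than an intention. The Safety Population difference is a real, unlisted departure from the protocol, probably of little practical effect.

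This should be fixed before database lock, because the choice of set affects the primary p-value and cannot credibly be settled after unblinding.

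**What to change.** Replace the deviation sentence in SAP 9 and revise the definitions:

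- **Efficacy (primary):** all randomized subjects who received at least one dose of study drug (REMD-477 or placebo) and have a baseline and at least one post-baseline insulin average, analysed as randomized, with no removal for deviations. This also replaces the undefined term evaluable. The data-availability condition is still a post-randomization one, but it is explicit and leaves no room for judgement.
- **Per-Protocol:** the only set that uses deviations, for one sensitivity analysis of the primary endpoint. List the excluding deviations in the SAP, and have membership fixed and documented before lock by staff without access to treatment codes.
- **Safety:** all subjects with at least one dose, as in Protocol Section 10.

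Add Efficacy to the populations named in SAP 10.1. The cost is SAP wording and one sensitivity table. The primary estimate may be slightly less favourable than one from a cleaned set.

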10 STATISTICAL METHODOLOGY

10.1 General

Data listings will be provided for the All Subjects Population. Summary statistics and statistical analyses will be performed for subjects included in the relevant analysis populations (Safety/PK/PD).

For continuous data, summary statistics will include the arithmetic mean, arithmetic standard deviation, median, minimum, maximum, and number. For log-normal data (eg, the Mixed Meal Tolerance Test [MMTT] parameters: areas under the concentration-time curve [AUCs]), the geometric mean and geometric coefficient of variation (CV%) will also be presented. For categorical data, frequency counts and percentages will be presented. Data listings will be provided for all subjects. For the calculation of summary statistics and statistical analysis, unrounded data will be used.

Outputs will be created separately for Parts A and B.

Missing values will not be imputed.

Data analysis will be performed using SAS® Version 9.4.

Analysis Data Model (ADaM) datasets will be prepared using Clinical Data Interchange Standards Consortium (CDISC) ADaM Version 2.1, and CDISC ADaM Implementation Guide Version 1.1. Pinnacle 21 Community Validator Version 2.2.0 will be utilized to ensure compliance with CDISC standards.

10.1.1 Definition of Baseline and Change from Baseline

Unless otherwise stated, the baseline for each parameter is defined as the last value measured prior to first dosing, including repeat (vital signs and electrocardiograms [ECGs]) and unscheduled (clinical laboratory parameters) readings (see Section 10.1.2 for definitions of repeat and unscheduled readings). For ECGs taken in triplicate, baseline will be the mean of the last three values taken prior to first dosing.

Mean change from baseline is the mean of all individual subjects' change from baseline values. Each individual change from baseline will be calculated by subtracting the individual subject's baseline value from the value at the timepoint. The individual subject's change from baseline values will be used to calculate the mean change from baseline using a SAS procedure such as Proc Univariate.

Mean percent change from baseline is the mean of all individual subjects' percent change from baseline values. Each percent change from baseline will be calculated by subtracting the individual subject's baseline value from the value at the desired timepoint and then dividing this calculated value by the individual subject's baseline value and multiplying by 100. These individual subjects' percent changes from baseline values will be used to calculate the mean percent change from baseline using a SAS procedure such as Proc Univariate.

10.1.2 Repeat and Unscheduled Readings

Repeat readings occur when the original vital signs or ECG result requires confirmation. Repeat readings are labelled as 'Repeat' in the listings and replace the original readings in all summaries and changes from baseline presentations and calculations. Prior to dosing, all readings taken in addition to the original reading are defined as pre-dose repeats. Post-dose repeat readings are defined as readings collected within 15 minutes of the actual time of the original reading. Where results are taken in triplicate and repeated, the last three readings are used in all subsequent calculations.

All results not taken at a scheduled timepoint for other data types (eg, clinical laboratory parameters) are unscheduled. Unscheduled readings are labelled as 'Unscheduled' in the listings. Because unscheduled readings are not associated with any scheduled timepoint, they are excluded from all summaries (with the exception that they may be used as baseline, as stated in Section 10.1.1).

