Study recruitment, progress and safety issues will be reviewed by the investigators, research nurse and research coordinators and communicated to the sponsor on a regular basis. The following will be reviewed: 1) subject enrollment, 2) preliminary findings that might affect the risk/benefit ratio or alter the procedures described in the protocol, 3) any clinically-significant out-of-range laboratory value and a course of action, and 4) any adverse or serious adverse events that might result from the research procedures.

The Safety Review Committee will review all available safety and PD data periodically during the study when approximately 33%, 66%, and 100% of the subjects in Part A have received a randomized treatment. After each safety data review, the Safety Review Committee will decide whether or not to continue with subject enrollment and dosing. Decisions to continue enrollment will be documented in the Safety Review Memo. REMD Biotherapeutics will issue a written notification of these decisions to investigators.

Determination of Adverse Event Severity and Relatedness

Adverse events will be coded per current MedDRA. Determination of the severity of adverse events will be consistent with Common Terminology Criteria for Adverse Events (CTCAE) V. 4.03. The relationship of an adverse event to treatment will be determined by the Investigator (see section 9: Reporting Procedures for All Adverse Events).

Dose Stopping Rules

Dosing will be stopped or modified if treatment-related AEs, changes in vital signs, ECG, or clinical laboratory results are observed and these changes pose a significant health risk, in the opinion of the Sponsor, Principal Investigator or Medical Monitor.

Medically significant AEs considered to be related to the investigational product and serious adverse events considered to be related to study procedures will be followed until resolved or considered stable.

A subject may be terminated at any point in time at the discretion of the Sponsor, Principal Investigator or Medical Monitor.

Stopping Rules for an Individual Subject:

At any time during the study, the subject must discontinue study drug treatment, if one of the following events occur:

- An increase of AST and/or ALT (> 3x ULN) are observed in the presence of increased (> 2x ULN) alkaline phosphatase and/or total bilirubin.
- A sustained AST or ALT increase, defined as three consecutive values of AST and/or ALT greater than 5x ULN within a period of 14 days.

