Subjects will be instructed to titrate their basal insulin dose to achieve a pre-breakfast blood glucose level of 4.4-6.6 mmol/L (80-120 mg/dL) and to titrate their bolus insulin dose to achieve a pre-lunch, pre-dinner, and bedtime blood glucose level of 4.4-6.6 mmol/L (80-120 mg/dL). Algorithms for titrating basal and bolus insulin doses to achieve target glycemic goals will be provided. Subjects' basal and bolus doses may also be adjusted at the discretion of the investigator's typical standard of care.

Adverse events and concomitant medications (including non-prescription medications and/or supplements such as protein / amino acid supplements) will be collected throughout the study when reported. Any rescue medications and use of meals/food to manage hypoglycemic sensations or events will be reviewed carefully with the subject and recorded accordingly. If there is a clinically significant laboratory abnormality or adverse event in need of monitoring, subjects will be followed until resolution of the abnormality or adverse event or until it is considered stable.

For subjects participating in Part A, CGM data will be collected throughout the study from Dose 1 through the End of Study Visit, and CGM devices will be "unblinded". For on-going or newly enrolled subjects in Part A at the time of Protocol Amendment #2, CGM data will be collected throughout the study from Dose 1 through the Day 85/Week 13 Visit, and CGM devices will be "unblinded". For subjects participating in Part B, CGM devices will be configured in a "blinded" fashion, wherein the CGM data will not be accessible to the subject or the Investigator, and will be collected for one week intervals during specified time periods noted in the [Schedule of Assessments – Part B](#) (study weeks 1, 4, 8, and 12, after receiving that week's assigned dose).

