Fasting Plasma Glucose	2	15	30
Fasting Lipid Panel	5	9	45
Serum PK sample collection	4	6	24
Serum FSH levels (women only) ^Φ	5	1	5 ^Φ
HbA1c	6	4	24
Plasma Glucose via YSI	NA	NA	NA
MMTT (glucose & insulin)	40	2	80
GLP-1 (active & total), Glucagon, Plasma insulin and C-peptide	4	6	24
Anti-REMD-477 Ab sample collection *	10 (first) / 5	3	20
Exploratory biomarker collection	30	3	90
Serum Ketones & free fatty acids	1.5	15	22.5
TOTAL**			404.5 409.5^Φ

* First collection is 10 mL, subsequent collections are 5 mL.

** Volume to be collected over approximately 238 days.

Table 7-3: Total Blood Volume for samples collected under Protocol Amendment #2, for subjects participating in Part B

Procedure	Volume per Collection (mL)	Number of Collections	Total Volume (mL)
Safety (chemistry + hematology)	5	9	45
Fasting Plasma Glucose	2	15	30
Fasting Lipid Panel	5	9	45
Serum PK sample collection	4	6	24
Serum FSH levels (women only) ^Φ	5	1	5 ^Φ
HbA1c	6	5	30
GLP-1 (active & total), Glucagon, Plasma insulin and C-peptide	4	6	24
Anti-REMD-477 Ab sample collection *	10 (first) / 5	3	20
Exploratory biomarker collection	30	3	90
Serum Ketones & free fatty acids	1.5	15	22.5
Liver Injury Biomarkers	10	5	50
TOTAL**			380.5 385.5^Φ

* First collection is 10 mL, subsequent collections are 5 mL.

** Volume to be collected over approximately 224 days.

Laboratory Safety Tests

Blood and urine samples for laboratory safety tests (clinical chemistry, hematology, and urinalysis) will be collected according to the Schedule of Assessments ([Appendix A](#)).

The date and time of blood and urine collection will be recorded in the subject's source documentation. The tests will be analyzed using standard procedures. White blood cell differentials will be reported in absolute counts.

All laboratory tests must be reviewed by the Principal Investigator or qualified designee prior to the subject receiving each dose. Additional safety laboratory assessments may be performed if clinically indicated.

The following analytes will be tested:

Chemistry

Albumin	Blood urea nitrogen (BUN)
Calcium	Chloride
Glucose	Phosphorus
Potassium	Serum creatinine
Magnesium	Sodium
Bicarbonate	Uric acid
Aspartate aminotransferase (AST)	Alanine aminotransferase (ALT)
Cholesterol	Lactate dehydrogenase (LDH)
Alkaline phosphatase (ALP)	Total bilirubin
Total protein	Direct bilirubin
HDL, LDL, Triglycerides	Total globulin

Hematology

Red blood cells (RBC)
Hemoglobin (Hgb)
Hematocrit (Hct)
Mean corpuscular volume (MCV)

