MRI-PDFF scans may be sent to a central imaging vendor for independent evaluation of liver fat content. The central radiologist should not have access to the treatment assignments or knowledge of whether the scans are performed at baseline or post-treatment for each patient.

Liver FibroScan®

A FibroScan® is a specialized ultrasound machine that measures fibrosis (scarring) and steatosis (fatty change) in the liver. For a subset of subjects in Part B only, sites that have access to a FibroScan® may elect to perform a FibroScan® prior to dosing on Day 1 (or up to 7 days before Day 1, after all other inclusion and exclusion criteria have been met) and on Day 85 (+/- 2 days) of Week 13. Scans will also be performed at the first occurrence of serum AST or ALT increase >3 xULN.

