10.4.2 Clinical Laboratory Parameters

Biochemistry and hematology data will be summarized separately for Parts A and B by treatment. Changes from baseline will be calculated.

Values for any biochemistry, hematology, and urinalysis values outside the clinical reference ranges will be flagged on the individual subject data listings.

AST, ALT, total and direct bilirubin will be summarized by treatment and timepoint. Changes from baseline will also be summarized.

The frequency of subjects who have a maximum ALT $>3x$ ULN for any post-dose timepoint will be presented by treatment group. Additionally, the frequency of subjects who have an ALT $> 3x$ ULN will also be presented for each assessment timepoint and treatment group. Similar tables shall also be presented for $>5x$ ULN and $>10x$ ULN. These frequency displays will also be provided for AST. The incidence of subjects who also have $>3x$ ULN increases in ALT and/or AST with $>2x$ ULN of total bilirubin will also be summarized by timepoint and treatment group.

A repeated measures ANCOVA will be used to compare the change from baseline in LDL cholesterol results between treatment groups on each day for Parts A and B separately. Dependent variables will be treatment, day, and the treatment by day interaction. The baseline variable will be used as a covariate.

Subject will be used as a random effect. The LS means for each treatment will be presented for each timepoint. Also, the difference from placebo, the 95% confidence interval of the difference from placebo, and p-value associated with the null-hypothesis of no difference will be for each day.

The SAS code will be similar to as shown below:

```
proc mixed data=xxx;
class subject day treatment;
model variable = baseline subject treatment day treatment*day;
repeated day / subject=subject type=csh;
lsmeans treatment*day / pdiff cl alpha=0.10;
ods output lsmeans=lsm;
ods output diffs=diff;
run;
```

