10.4.4 Electrocardiogram

The ECG data will be obtained directly from the 12-lead ECG traces. These data include the QT interval calculated using the Bazett correction (QTcB), the QT interval calculated using the Fridericia correction (QTcF), the PR and QT intervals, the QRS duration, heart rate, and RR.

The ECG data will be summarized separately for Parts A and B by treatment, together with changes from baseline (see Section 10.1.1 for definitions of baseline). Figures of mean ECG data and mean change from baseline profiles will be presented separately for Parts A and B by treatment. The relationship between plasma concentrations of REMD-477 and changes from baseline in QTcF and QTcB will be explored graphically.

An outlier analysis will be performed including all individual post-dose QTcF and QTcB measurements (not the mean data), including all repeat and unscheduled readings. The frequency of subjects with a maximum increase from baseline in QTcB and QTcF intervals will be summarized for each treatment according to the following categories: >30 to 60 ms, >60, and \leq 30 ms. All incidences of >30 to \leq 60 ms, and >60 ms will be flagged on the listing. In addition, the frequency of subjects with QTcB and QTcF post-dose values will be summarized for each treatment, according to the following categories: >450 to 480, >480 to 500, >500, and \leq 450 ms. All incidences of >450 to 480, >480 to 500, and >500 ms will be flagged on the listing.

For Parts A and B separately the change from baseline of QT interval will be analyzed with a repeated measures ANCOVA. Dependent variables will be treatment, timepoint and the treatment by timepoint interaction. The change from baseline of the RR interval will serve as a covariate. Day is fitted as a repeated measure within subject. The estimated treatment means of the change from baseline of QT interval when change in RR interval equals zero will be presented for each timepoint. Also, the difference from placebo, the 95% CI of the difference from placebo, and p-value associated with the null-hypothesis of no difference will be presented for each timepoint.

An example of the SAS codes (abbreviated) is shown below:

```
proc mixed data=xxx;
  class subject day trtan;
```

```
model chg = chg_rr subject trtan day treatment*day;
repeated day / subject=subject type=csh;
lsmeans trtan*day / pdiff cl alpha=0.05;
estimate 'Est_CFB RR=0' intercept 1 chg_rr 0 trtan 1 0 avisit 1 0 0
trtan*avisit 1 0 0 0 0 0 /e;
...
run;
```

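### The liver threshold tables leave out unscheduled ALT, AST and bilirubin values, so they show each subject's worst scheduled value, not the worst value

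*SAP*

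**What the plan says.** SAP 10.1.2 separates two kinds of extra reading. Repeats of vital signs and ECGs replace the original value. For other data, with clinical laboratory parameters given as the example, any result not taken at a scheduled timepoint is unscheduled, and the rule is: "Because unscheduled readings are not associated with any scheduled timepoint, they are excluded from all summaries". The only stated exception lets such a reading serve as baseline.

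SAP 10.4.2 then plans these liver displays:

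- subjects whose maximum ALT exceeds 3x ULN, "for any post-dose timepoint will be presented by treatment group", repeated for 5x and 10x ULN and for AST;
- the same thresholds counted at each assessment timepoint;
- subjects with ALT and/or AST above 3x ULN together with a value above 2x ULN "of total bilirubin will also be summarized by timepoint and treatment group".

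Unscheduled readings are not mentioned there. Out-of-range values are flagged in the subject listings. SAP section 12 adds no exception. SAP 10.4.4 does add one for the QTc outlier analysis, which takes all individual post-dose "measurements (not the mean data), including all repeat and unscheduled readings".

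The protocol provides for off-schedule chemistry. Section 7, Laboratory Safety Tests: "Additional safety laboratory assessments may be performed if clinically indicated". Section 7, Throughout the Study: "If there is a clinically significant laboratory abnormality or adverse event in need of monitoring, subjects will be followed until resolution of the abnormality". Two protocol actions depend on liver values whenever they are drawn. Under Liver FibroScan (Part B, participating sites): "Scans will also be performed at the first occurrence of serum AST or ALT increase" above 3x ULN. Under the individual stopping rules in section 6, a sustained rise is defined as "three consecutive values of AST and/or ALT greater than 5x ULN within a period of 14 days".

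**The concern.** A table of per-subject maxima is where a reader looks for the worst liver value in each arm. Under 10.1.2 it holds the worst scheduled value instead.

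Transaminase elevation is the known laboratory signal for this antibody. Protocol section 2 reports ALT rises up to 3x ULN in 7 of 12 patients in the 70 mg cohort of the type 2 diabetes study, plus one isolated value of 18x ULN at a single time. A short peak of that kind is easily missed by sparse scheduled draws and may be seen only on an extra one.

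A subject could trigger a FibroScan, or be stopped under the 5x ULN rule, on unscheduled values and not appear in the matching >3x or >5x table. Tables and listings would then disagree. Adverse event tables are not a sure backstop, because protocol section 9 generally keeps laboratory findings judged not clinically significant out of the adverse event record.

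**Working it through.** The plan gives no figure to reproduce. The check compares the text rules and then works out how far the protocol relies on unscheduled draws.

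**1. Text.** 10.1.2 names laboratory data and covers all summaries. The baseline exception cannot bring back a post-dose value. 10.4.2 and section 12 contain no override, and 10.4.4 does. The exclusion therefore governs the liver tables.

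**2. Scheduled post-dose chemistry** (protocol Appendix A, both Parts): Days 8, 15, 29, 43 and 57 (each ±1), 85 and 162 (each ±2). In Part A the last draw falls in the Day 161/162 end-of-study visit. Check: screening + baseline + 7 = 9, which matches the 9 safety collections in Tables 7-1 to 7-3.

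**3. Coverage of visits.** Visits after Day 1: 11 dosing visits + Days 85, 106, 134 and 162 = 15. Chemistry is scheduled at 7. The other 8 are Days 22, 36, 50, 64, 71, 78, 106 and 134, and 6 of these are dosing visits.

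**4. Span of three consecutive scheduled draws.** Nominal span = last day − first day. Minimum span = (last day − its window) − (first day + its window).

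| Draws | Nominal (days) | Minimum (days) |
|---|---|---|
| 8, 15, 29 | 29 − 8 = 21 | 28 − 9 = 19 |
| 15, 29, 43 | 28 | 26 |
| 29, 43, 57 | 28 | 26 |
| 43, 57, 85 | 42 | 83 − 44 = 39 |
| 57, 85, 162 | 105 | 160 − 58 = 102 |

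All exceed 14 days. A post-dose run that meets the 14-day rule therefore contains at least one unscheduled value.

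**5. Gaps between adjacent draws**, nominal (minimum): 7 (5), 14 (12), 14 (12), 14 (12), 28 (25), 77 (73). From the Day 57 draw onward, a 14-day period holds at most one scheduled draw, so at least two of the three values must be unscheduled.

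**6. When a subject, not just a value, is lost.** The three values are consecutive, so a scheduled draw inside the run is itself above 5x ULN and puts the subject in the >5x table. A stopped subject is absent from that table only if all three values are unscheduled and no other scheduled post-dose value exceeds 5x ULN. For any single threshold, the subject is absent if the only crossing is on an unscheduled draw.

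**7. Chance that a short rise meets a scheduled draw.** The documents give no duration, so this is an assumption: onset uniform over Days 2 to 85 (84 days), elevation lasting L days. The share of onsets that meet a scheduled draw is:

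- L = 3: 18/84 = 21%
- L = 7: 42/84 = 50%
- L = 14: 70/84 = 83%

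This says nothing about whether an unscheduled draw would be taken.

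**8. Scale.** One subject in an arm of 25: 1/25 = 4 percentage points.

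**The case against.** The strongest objection is that omitting a value is not omitting a subject. Extra draws usually follow an abnormality already seen. If that first value was a scheduled one above 3x ULN, the subject is already in the >3x table. This stands. Steps 4 and 5 show that the stopping rule depends on unscheduled values; they do not show that stopped subjects vanish. The possible loss is a crossing first seen off schedule, or a retest that climbs into a higher category.

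Second, the any-timepoint wording of the maximum table, set against a separate by-timepoint count, could be read to take in every draw. The reason given in 10.1.2 also fits by-visit summaries better than subject maxima. That reading is possible, but it conflicts with an exclusion from all summaries, and two programmers could build different tables. It cannot help the combined bilirubin table, which is by timepoint only: a subject with both elevations on one unscheduled draw is not counted.

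Third, the QTc wording may be there because ECG repeats replace originals, so its absence for laboratory data is limited evidence of intent. That is fair. The finding rests on the general rule, not on intent.

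Fourth, the table shells were not available and might settle the matter. The listings, the Safety Review Committee and the adverse event outputs still show these cases. That limits the harm but does not correct the tables.

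**Conclusion.** The concern holds and should be fixed. As written, the per-subject maximum ALT and AST tables and the combined ALT/AST-plus-bilirubin table use scheduled draws only, and can undercount the main known safety signal by arm.

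The size cannot be computed from the documents and may be zero; each subject missed is about 4 percentage points of an arm of 25. No primary result, power figure or error rate is affected, and the values stay in the listings. The conclusion assumes that 10.1.2 is applied as it reads and that no table shell overrides it.

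**What to change.** Add to SAP 10.4.2 that the per-subject maximum ALT and AST tables (>3x, >5x, >10x ULN) use every post-dose value, scheduled or unscheduled. Add one per-subject table, on the same basis, of ALT and/or AST above 3x ULN with total bilirubin above 2x ULN at any time after dosing. Keep the by-visit summaries and by-timepoint counts on scheduled draws. Add a cross-reference in 10.1.2 so that the two sections agree.

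This follows the approach the SAP already takes for QTc outliers and changes no clinical rule. The cost is one or two sentences, a small programming change and one extra table; the data are already collected and listed.
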